6.2 DETAILS OF TRIAL PROCEDURES AT SELECTED VISITS

The investigations as outlined in the Flow Chart will be performed at the respective visits.

Specific details to conduct of physical examination, collection of vital signs (including blood pressure measurement), laboratory investigations, assessment of ECG and echocardiography can be found in Section 5.3.

Page 53 of 99

Trial Protocol Proprietary confidential information © 2019 Boehringer Ingelheim International GmbH or one or more of its affiliated companies

After the interim data base lock, mandatory procedures/assessments and documentation in the eCRF will be adapted as described in the Flow Chart and the respective sections of this protocol.

6.2.1 Screening period

All Screening Visit procedures must be performed in the 21 days prior to the first administration of study medication except tumor assessments (CT/MRI) that may be used as screening exams if they were performed within 28 days prior to start of treatment.

Echocardiography must be obtained within 7 days before start of treatment.

Patients who meet the eligibility criteria will be allowed to take part to the study. Refer to the Flow Chart for procedure details. Please review Sections 3.3.2 and 3.3.3 for specific eligibility criteria.

6.2.2 Treatment period(s)

All patients will receive continuous weekly treatment with BI 836880 until the criteria for stopping medication are met (see Section 3.3.4).

Treatment course is defined as 3-week treatment (21 days) in duration. During the treatment phase visits should be performed as scheduled wherever possible.

In the event of any study drug interruption or delay of treatment, the tumor assessment scheduled will not be changed.

After the interim data base lock, frequency of tumor assessment may be adapted according to local standard of care and in agreement with the sponsor if the patient is deriving clinical benefit (e.g. CR, PR or SD > 6 months).

Additional visits are needed at day 2 for courses 1, 2 and 4. For course 3 and from course 5 onwards no additional visits, beside day 1 including drug administration, are requested by protocol.

Refer to the Flow Chart for procedure details.

Follow Up Period and Trial Completion 6.2.3

6.2.3.1 End of treatment visit

The EOT visit will be performed after permanent discontinuation of trial medication for any Reason, as soon as possible, but no later than 21 days after permanent discontinuation of the trial medication or when the investigator decided with the patient to permanently discontinue the trial medication or became aware that the trial medication had been terminated.

Page 54 of 99

Proprietary confidential information © 2019 Boehringer Ingelheim International GmbH or one or more of its affiliated companies

6.2.3.2 Residual effect period (REP)

The REP is defined in Section 5.3.6.2. The End of the Residual period visit (EoR) should not be performed earlier than 42 days after permanent discontinuation of the study drug. The information collected at this visit should include all new AEs that occurred after EOT and a follow-up of adverse events ongoing at EOT. Any subsequent anti-cancer therapy administered between EOT and EoR should be reported.

6.2.3.3 Follow-up period for progression

For patients who progress according to RECIST criteria V1.1, one Follow up visit (FU1) will be performed after the EOT (i.e. at EoR, 42 calendar days after discontinuation of trial drug).

For patient who discontinue not due to progressive disease according to RECIST criteria V1.1, additional FU visits will be performed at 6-week intervals plus/minus 3 days, until progression, start of another anticancer treatment, lost to follow up, death.

After the interim data base lock, frequency of tumor assessment may be adapted according to local standard of care and in agreement with the sponsor if the patient is deriving clinical benefit (e.g. CR, PR or SD > 6 months).

During extended Follow up period (i.e. after the end of treatment, including the REP and individual patient's end of trial), all related SAEs or AESIs and Follow up AEs on going since the end of treatment have to be collected and documented on the appropriate eCRF page and SAE form (if applicable).

Refer to Flow Chart for details.

6.2.3.4 Trial completion for an individual patient

A patient is considered to have completed the trial in case any of the following applies:

- Completion of planned follow-up period (as defined in Section 6.2.3.3)
- Lost to follow-up
- Withdrawal to be followed-up
- Death

At the earliest of the above criteria, the Patient Completion information should be entered in the CRF.

6.2.3.5 Trial completion

The clinical trial will be considered completed when the last patient has completed the EoR visit. If patients are still on treatment at the time of interim data base lock and the Clinical Trial Report is written, these patients will be maintained in the trial as long as they are deriving clinical benefit (i.e. no disease progression, no drug-related AEs requiring drug discontinuation) or no new anti-cancer treatment started and there are willing to continue. For these patients, no blood sample will be collected for PK/PD and biomarker analysis, only (S)AEs and limited efficacy data will be collected. After the discontinuation of these patients, additional data collected after data base lock will be reported in separate listings and will not

Boehringer Ingelheim BI Trial No.: 1336.6 c03124055-06

Trial Protocol

Page 55 of 99

13 Mar 2019

Proprietary confidential information © 2019 Boehringer Ingelheim International GmbH or one or more of its affiliated companies

lead to any further update of tables generated for section 15 of the CTR unless deemed necessary. These listings will be included in a revised CTR.

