3.3.4 Removal of patients from therapy or assessments

3.3.4.1 Removal of individual patients

An individual patient is to be withdrawn from trial treatment if:

- The patient withdraws consent for study treatment or study participation, without the need to justify the decision.
- Requiring concomitant drugs that interfere with the investigational product or other trial medication (see Section 4.2.2) or patient who requires concomitant drugs, which in the opinion of the investigator may interfere with the investigational drug.
- The patient can no longer be treated with trial medication for other medical reasons (such as surgery, adverse events, other diseases, or pregnancy).
- The patient is no longer able to complete trial visit or trial-required procedures.
- A DLT occurs which does not recover to a degree that allows continuation of treatment (see Section 4.1.4) for re-treatment criteria and dose reduction scheme)
- Progressive disease (except in cases with intra-patient dose escalation, (see Section 4.1.3) or start of any new anti-cancer therapy.

A patient can have withdrawn from the trial after discussion between the Investigator and the Sponsor if eligibility criteria are violated and/or the patient fails to comply with the protocol.

All withdrawals will be documented and the reason for withdrawal recorded and discussed, as necessary, in the final Clinical Trial Report (CTR). As soon as a patient is withdrawn from the study treatment, the end of treatment visit (EoT) has to be performed if feasible. Every effort should be made to follow-up with patients in case an adverse event is still ongoing at the time of withdrawal. If a patient is withdrawn from the trial due to consent withdrawal, no further visit will be completed.

Patients who have not completed first course of BI 836880 treatment (3 weeks) for any other reason than BI 836880 related toxicities will be considered not evaluable for MTD evaluation and should be replaced.

Patient who prematurely discontinue study drug for above mentioned reasons or any other reason, should have additional follow up visits until progression, lost to follow up, treatment with another anti-cancer treatment, death and /or end of the trial whichever comes first.

Trial Protocol Page 28 of 99

Proprietary confidential information © 2019 Boehringer Ingelheim International GmbH or one or more of its affiliated companies

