4. TREATMENTS

4.1 TREATMENTS TO BE ADMINISTERED

4.1.1 Identity of BI investigational product(s) and comparator product(s)

Table 4.1.1: 1 Test product 1

Substance:	BI 836880
Pharmaceutical formulation:	solution for infusion after dilution
Source:	Boehringer Ingelheim Pharma GmbH & Co. KG
Unit strength:	10 mg/ml (vials with 10 ml)
Posology	rate controlled infusion
Route of administration:	i.v.
Duration of use	until progression disease or unacceptable toxicity

Table 4.1.1: 2 Diluent for Test product 1

Substance:	Diluent for BI 836880 drug product
Pharmaceutical formulation:	Diluent to prepare solution for infusion of BI 836880
Source:	Boehringer Ingelheim Pharma GmbH & Co. KG
Unit strength:	50 ml/vial
Posology	rate controlled infusion
Route of administration:	i.v.
Duration of use	until progression disease or unacceptable toxicity

Trial Protocol

Page 30 of 99

Proprietary confidential information © 2019 Boehringer Ingelheim International GmbH or one or more of its affiliated companies

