4.2.2 Restrictions

4.2.2.1 Restrictions regarding concomitant treatment

Previous anti-cancer therapy must have been discontinued before first administration of BI 836880 and the patient must have recovered from all clinical relevant reversible toxicities (see exclusion criteria in Section 3.3.3).

Concomitant anti-cancer therapy is not allowed.

Radiotherapy for local symptom control of non-target lesions can be allowed after discussion between the investigator and the sponsor. The irradiated area cannot be used for response assessment.

13 Mar 2019

Trial Protocol

Page 36 of 99

Proprietary confidential information © 2019 Boehringer Ingelheim International GmbH or one or more of its affiliated companies

Full-dose anticoagulation (according to local guidelines) with Vitamin K antagonist and other anticoagulation is not allowed during the trial conduct; LMWH is allowed only for prevention not for curative treatment.

Any planned surgeries are not allowed. Unplanned surgeries should be postponed whenever possible four weeks after stop of treatment. For urgent interventions patients should not be treated further and does require intense monitoring regarding wound healing and postoperative complications.

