c03124055-06

N. C		D 1 1 1 11 1		
Name of company:		Boehringer Ingelheim		
Name of finished product:		Not applicable		
Name of active ingredient	:	BI 836880		
Protocol date:	Trial number:		Revision date:	
10 Dec 2015	1336.6		13 Mar 2019	
Main criteria for inclusion:	 Age ≥ 18 years Histologically or cytologically confirmed malignancy which is locally advanced or metastatic solid tumor, and either refractory after standard therapy for the disease or for which standard therapy is not reliably effective, e.g. patients do not tolerate or have contraindications to otherwise available standard therapy and tumour lesions evaluable for Dynamic contrast-enhanced (DCE) MRI at MTD ECOG performance status ≤2 Adequate hepatic, renal and bone marrow functions Life expectancy ≥ 3 months in the opinion of the investigator Recovery from all reversible adverse events of previous anti-cancer therapies to baseline or CTCAE grade 1, except for alopecia (any grade) and sensory peripheral neuropathy CTCAE grade < 2 			
Test product(s):	BI 836880 and Diluent for BI 836880			
dose:	Starting dose of 40 mg weekly infusion			
mode of administration:	Intravenous weekly in	a 21-day treatment course		
Comparator products:	Not applicable			
dose:	Not applicable			
mode of administration:	Not applicable			
Duration of treatment:	Continuous treatment in the absence of disease progression or unacceptable toxicity			
Endpoints	Primary endpoint			
Safety criteria:		ling to Common Terminology Crite se limiting toxicities, physical exam , ECOG		
Statistical methods:		ratory statistics analyses. Dose esca ession model with over dose control		

FLOW CHART COURSE 1

Trial periods	Screening	Treatment course***				ЕОТ*	EoR*	FU**	
Course			1						
Visit	Screen		V1		V2	V3			
Day	-21 to -1	1	2	3	8 + 2	15 + 2		EoT+42 d	
Informed consent ¹	x								
Demographics	x								
Medical history	X								
Inclusion/exclusion criteria	X	Х							
Physical examination ²	X	Х	х	X	X	х	Х	x	
Height	X								
Weight	X	Х					х		
Body temperature ³	x	Х	х		Х	х	Х		
Blood pressure ⁴ , heart rate	X	х	х	X	X	х	Х	х	
ECOG performance status	x	Х					Х		
Administration of BI 836880 infusion		Х			Х	х			
Safety Lab parameters ⁵	x	Х			Х	х	Х		
Pregnancy test	X	Х					Х		
Tumor assessment ⁶	x						Х		Х
12-lead ECG ⁷	x	х	х		Х	х	Х		
Echocardiography ⁸	x						х		
Pharmacokinetics ⁹		х	х	X	Х	х	х	Х	x (FU1)
Anti-drug antibodies ¹⁰		х					Х	х	x (FU1)

Trial Protocol

Page 5 of 99

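### The post-lock continuation rule in Protocol 6.2.3.5 uses *or* where 3.3.4.1 requires both conditions, so read literally it allows dosing past progression or alongside new anti-cancer therapy (minor effect)

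*Protocol*

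**What the plan says.** Section 6.2.3.5 (Trial completion) deals with patients still on treatment when the interim database is locked and the trial report is written. Such patients remain participants "as long as they are deriving clinical benefit (i.e. no disease progression, no drug-related AEs requiring drug discontinuation) or no new anti-cancer treatment started"; they must also be willing to continue. The section appears twice in the protocol file, with the same wording both times.

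The general stopping rule is in Section 3.3.4.1. It opens with "An individual patient is to be withdrawn from trial treatment if" and lists events, each sufficient by itself. One entry covers two of them: "Progressive disease (except in cases with intra-patient dose escalation", with a pointer to Section 4.1.3, and then "or start of any new anti-cancer therapy". The exception is attached to progression only. Other entries cover withdrawal of consent and medical reasons, including adverse events, that prevent further treatment.

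Other parts of the protocol agree with 3.3.4.1, and none has an exemption after the lock:

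- Section 6.2.2: "All patients will receive continuous weekly treatment with BI 836880 until the criteria for stopping medication are met (see Section 3.3.4").
- Synopsis, duration of treatment: "Continuous treatment in the absence of disease progression or unacceptable toxicity".
- Table 4.1.1: 1, duration of use: "until progression disease or unacceptable toxicity".
- Section 4.2.2.1: "Concomitant anti-cancer therapy is not allowed". This is a prohibition and does not itself order withdrawal.
- Section 3.1 and the Flow Chart note on treatment courses also tie continued treatment to the criteria in 3.3.4.

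**The concern.** The bracket in 6.2.3.5 defines clinical benefit as no progression and no drug-related adverse event that requires stopping. It closes before the *or*. Absence of new anti-cancer treatment is therefore not part of the definition. It is a second, alternative ground for staying.

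Read that way, a willing patient could continue (a) after progression, if no new therapy has begun, or (b) after new therapy has begun, while still benefiting. Both contradict 3.3.4.1, and (b) also sits badly with 4.2.2.1.

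At stake is a dosing rule for an investigational drug in the period when the protocol mandates least monitoring. After the lock, the Flow Chart notes make physical examination, ECOG status, body temperature and blood pressure non-mandatory at specific visits. Safety laboratory tests are at the investigator's discretion and ECGs are done as clinically indicated. Section 6.2.3.5 is the passage written for these patients, so it is the one a site would consult.

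**Working it through.** No figure in the plan is involved. The check compares the two rules case by case.

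**Inputs**

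- P = progression; D = drug-related adverse event requiring discontinuation; N = new anti-cancer therapy started; W = willing to continue.
- Section 6.2.3.5 as written: benefit is (not P and not D). Continuation is benefit *or* (not N), *and* W.
- Section 3.3.4.1: continue only if not P, not D and not N. With intra-patient dose escalation, P is excepted, so continue if not D and not N. D is covered by the entry on medical reasons, including adverse events.

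The sentence can be grouped as [benefit or (not N)] and W, or as benefit or [(not N) and W]. For a willing patient (W true) the two groupings give the same result, so the ambiguity does not matter here.

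**Cases for a willing patient**

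| P | D | N | 6.2.3.5 as written | 3.3.4.1 | 3.3.4.1 with escalation | *and* in place of *or* |
|---|---|---|---|---|---|---|
| no | no | no | continue | continue | continue | continue |
| yes | no | no | continue | stop | continue | stop |
| no | no | yes | continue | stop | stop | stop |
| yes | no | yes | stop | stop | stop | stop |
| no | yes | no | continue | stop | stop | stop |
| yes | yes | no | continue | stop | stop | stop |
| no | yes | yes | stop | stop | stop | stop |
| yes | yes | yes | stop | stop | stop | stop |

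**Counts**

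- First four rows (no adverse event requiring discontinuation): 6.2.3.5 and 3.3.4.1 differ in 2 of 4 (progression only; new therapy only). With escalation they differ in 1 of 4 (new therapy only).
- All eight rows: 6.2.3.5 allows continuation in 5 of 8 and 3.3.4.1 in 1 of 8, so they differ in 5 − 1 = 4. With escalation 3.3.4.1 allows 2 of 8, and they differ in 5 − 2 = 3. The subtraction is valid because every state that 3.3.4.1 allows is also allowed by 6.2.3.5.
- The eight-row count shows a further literal consequence: a patient with a drug-related adverse event requiring discontinuation could stay on if no new therapy had started.
- Replacing *or* with *and*: 0 differences without escalation, 1 with it (progression only). A one-word change would remove the escalation exception for these patients.
- Cross-reference to 3.3.4.1: 0 differences in every case, by construction.

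These are counts of logical states, not of patients or of risk.

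**Does the sentence govern dosing?** It speaks of being kept in the trial, whereas 3.3.4.1 governs trial treatment. A patient can be off drug and still in the trial until the end-of-residual-effect visit, and Section 6.2.3.2 expects that new anti-cancer therapy may be given in that window. Within 6.2.3.5, however, the patients are defined as being on treatment, they must be willing to continue, and the next sentences refer to their later discontinuation. The Flow Chart also drops additional follow-up visits after the lock. Together these favour reading the sentence as continued dosing.

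**The case against.** The strongest reply is that 6.2.3.5 is a trial-completion section and does not claim to amend the stopping rules. Those are set in 3.3.4.1 and repeated in Section 3.1, the Flow Chart note on treatment courses and Section 6.2.2, none with an exemption after the lock. A site following the whole protocol would still stop dosing in both cases. On this view the sentence is a loosely drafted list of stopping events whose intended word is plainly *and*. The post-lock data go to separate listings, and nothing in the SAP depends on it.

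The monitoring point also needs balance. Adverse events and limited efficacy data are still collected after the lock. Tumour assessments may be made less frequent only with the sponsor's agreement and only for a patient deriving benefit, so that relaxation does not reach a patient who has progressed.

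Most of this stands, and it is why the effect is minor. It does not make the sentence right. That the other sections all say otherwise shows that 6.2.3.5 is the inconsistent one. It is also the specific rule for this group and period, and a reader may take a specific rule as overriding a general one. If the intent was *and*, correcting the text removes the doubt at no cost.

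**Conclusion.** The point holds. As written, 6.2.3.5 contradicts 3.3.4.1 for a willing patient with progression alone (outside intra-patient dose escalation) or with new anti-cancer therapy alone.

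The effect is minor. Section 3.3.4.1 remains in force for all patients, and the synopsis and Table 4.1.1: 1 also stop treatment at progression. The MTD is unaffected, because it uses DLTs in the first course (Protocol 5.1.1 and 7.3.1; SAP 5.1). The documents do not give the number of patients on drug at the lock, so the number exposed to the ambiguity cannot be estimated.

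The conclusion rests on two readings: that the *or* is taken literally, and that staying in the trial means continued dosing. The first follows from the position of the bracket; the second is supported by the surrounding sentences but not stated outright.

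**What to change.** Replace the condition in 6.2.3.5 with: *these patients may continue study treatment as long as none of the withdrawal criteria in Section 3.3.4.1 is met; after discontinuation they complete the EOT and EoR visits.*

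This keeps the intra-patient dose-escalation exception, which a bare change to *and* would lose. It also covers adverse events and withdrawal of consent through the existing list, and does not end trial participation before the EoR visit. The cost is one sentence in the next amendment, with no change to data collection or analysis.

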7. STATISTICAL METHODS AND DETERMINATION OF SAMPLE SIZE

7.1 STATISTICAL DESIGN – MODEL

This is phase I, open-label, dose-escalating trial to determine the MTD and RP2D for BI 836880 in patients with solid tumors. MTD is defined as the highest dose with less than 25% risk of the true DLT probability being above 33%, and may be considered reached if the probability that the true DLT rate is in target interval (16%-33%) is sufficiently large. Dose escalation and determination of MTD will be guided by a Bayesian 2-parameter logistic regression model with overdose control (R13-4803, R13-4806). These designs have been shown to be superior regarding the precision of MTD determination compared to 3+3 designs and have been particularly endorsed by the FDA (R13-4881).

The model is formulated as follows:

 $logit(p(d)) = log(\alpha) + \beta * log(d/d*),$

where logit(p) = log(p/(1-p)).

p(d) represents the probability of having a DLT in the first course at dose d, $d^* = 1250$ mg is the reference dose, allowing for the interpretation of α as the odds of a DLT at dose d^* , and $\theta = (\log(\alpha), \log(\beta))$ with α , $\beta > 0$ is the parameter vector of the model.

Since a Bayesian approach is applied, a prior distribution $\pi(\theta)$ for the unknown parameter vector θ needs to be specified. This prior distribution will be specified as a mixture of three multivariate normal distributions, i.e.

$$\pi(\theta) = \phi_1 \pi_1(\theta) + \phi_2 \pi_2(\theta) + \phi_3 \pi_3(\theta)$$

with

 $\phi_i,\,i=1,\,2,\,3$ the prior mixture weights $(\phi_1+\,\phi_2+\,\phi_3=1)$

and

$$\pi_i(\theta) = MVN(\mu_i, \Sigma_i)$$

the multivariate normal distribution of the i-th component with mean vector μ_i and covariance matrix Σ_i , with

$$\Sigma_{i} = \begin{pmatrix} \sigma_{i,11}^{2} & \sigma_{i,11}\sigma_{i,22}\rho_{i} \\ \sigma_{i,11}\sigma_{i,22}\rho_{i} & \sigma_{i,22}^{2} \end{pmatrix}$$

Mixture prior distributions have the advantage that they allow for specification of different logistic dose-toxicity curves, therefore making the prior more robust.

Prior derivation

For the current study, no relevant information in the form of human data was available, since no study in a comparable population has been conducted. Therefore, the three mixture components were established as follows:

1. A weakly informative prior was derived to reflect a priori assumption that the median DLT rate at the starting dose of 40mg would equal 0.1%, and the median DLT rate at the anticipated MTD of 480mg would equal 20%. This yields $\mu_1 = (0.740, 0.798)$. The standard deviations were set such that large uncertainty about the parameter means is

reflected, and the correlation was set to 0, thus yielding $\sigma_{1,11} = 2$, $\sigma_{1,22} = 1$ and $\rho_1 = 0$, respectively. The prior weight ϕ_1 for the first component was chosen as 0.9.

- 2. A high-toxicity weakly informative prior was derived to reflect the case that the compound would be much more toxic than expected. For this prior component, it was assumed that the median DLT rate at the starting dose of 40mg would equal 10%, and the median DLT at the anticipated MTD of 480mg would equal 50%. These assumptions yield $\mu_2 = (0.846, -0.123)$. The standard deviations and correlations were set identical to the weakly informative prior, i.e. $\sigma_{2,11} = 2$, $\sigma_{2,22} = 1$ and $\rho_2 = 0$, respectively. The prior weight ϕ_2 for the second component was chosen as 0.05.
- 3. A low-toxicity weakly informative prior was derived to reflect the case that the compound would be much less toxic than expected. For this prior component, it was assumed that the median DLT rate at the starting dose of 40mg would equal 0.1%, and the median DLT at the anticipated MTD of 480mg would equal 2%. These assumptions yield $\mu_3 = (-2.731, 0.193)$, i.e. basically a flat curve. The standard deviations and correlations were set to $\sigma_{3,11} = 5$, $\sigma_{3,22} = 0.01$, therefore almost fixing the slope parameter to its mean. The correlation was set to 0, i.e. $\rho_3 = 0$. The prior weight ϕ_3 for the third component was chosen as 0.05.

A summary of the prior distribution is provided in Table 7.1:1. Additionally, the prior probabilities of DLT at different doses, as well as the corresponding probability of under-, targeted and overdosing, are shown in Table 7.1:2. Graphically, the prior medians with accompanying 95% credible intervals are shown in Figure 7.1:1. As can be seen from both, the Table and the Figure, the prior medians of the DLT probabilities are in-line with the prior medians derived from the weakly informative prior, and the uncertainty around the medians is large, showing the low amount of information this prior provides. This is also supported by the prior sample size, i.e. the information contained in the prior. This is approximately equal to 1 patient, i.e. less than or around half of the weight the first cohort in the study will have.

Table 7.1: 1 Summary of prior distribution

Prior Component	Mixture Weight	Mean vector	SD vector	Correlation
1: Weakly inf.	0.900	0.740, 0.798	2.000, 1.000	0.000
2: High Tox	0.050	0.846, -0.123	2.000, 1.000	0.000
3: Low Tox	0.050	-2.731, 0.193	5.000, 0.010	0.000

Table 7.1: 2 Prior probabilities of DLT at selected doses

Dose	Probability of true DLT rate in					Quantiles		
	[0-0.16)	[0.16-0.33)	[0.33-1]	Mean	SD	2.5%	50%	97.5%
40	0.842	0.054	0.104	0.091	0.206	<.001	0.001	0.819
120	0.759	0.076	0.165	0.139	0.249	<.001	0.009	0.897
240	0.673	0.096	0.231	0.193	0.282	<.001	0.036	0.935
480	0.523	0.131	0.346	0.284	0.318	<.001	0.138	0.964
960	0.262	0.143	0.595	0.471	0.332	0.002	0.458	0.984
1250	0.142	0.114	0.744	0.594	0.316	0.012	0.659	0.991

Doses printed in bold face meet the overdose criterion (P(overdose) ≤ 0.25))

c03124055-06

Proprietary confidential information © 2019 Boehringer Ingelheim International GmbH or one or more of its affiliated companies

Median (95% Crl)

[figure not shown]

Figure 7.1: 1Prior medians and 95% credible intervals

The MTD may be considered reached if the following criteria are fulfilled:

- 1. At least 1 DLT on the trial and either
- 2. At least 6 patients haven been treated at the MTD and the posterior probability of the true DLT rate in the target interval (16%-33%) is above 50%, OR
- 3. At least 18 patients in the trial with 6 patients have been treated at MTD.

Statistical model assessment:

The model was assessed using two different metrics:

